5. TRIAL OBJECTIVES AND PURPOSE

The overall purpose of this Phase 1 study is to explore the safety and tolerability of LAM-002A when given alone and in combination for the treatment of subjects with relapsed or refractory B-cell NHL.

5.3. Exploratory Objectives

- To evaluate the pharmacodynamic effects of LAM-002A, administered orally, in plasma assays and on surrogate tissue (e.g., vacuoles in peripheral blood smears, gene expression in peripheral blood mononuclear cells [PBMCs]/B cells, and plasma cytokines [including (IL)-12 and IL-23]).
- To evaluate tumor for gene expression and genetic alterations (with saliva and/or B-cell-depleted PBMC collection for germ-line control) and surrogate tissue (PBMC/B cells) for gene expression that may predict anti-lymphoma activity.
- To evaluate plasma for changes in analytes **or tumor for protein expression** that may predict anti-lymphoma activity.

5.6. Exploratory Endpoints

- Extent of PIKfyve inhibition as determined by plasma inhibitory assaysthe extent of vacuole formation in white blood cells in peripheral blood smears by microscopic evaluation
- Changes in gene expression in PBMCs
- Changes in plasma cytokines (including IL-12 and IL-23)
- Correlation between genetic alterations as determined by next generation sequencing and/or gene expression in tumor tissue, **circulating tumor DNA**, or PBMCs/B **cells** and anti-lymphoma activity following treatment with LAM-002A

Version 9, 18 Feb 2020

 Correlation between changes in plasma bioanalytes or tumor protein expression and anti-lymphoma activity following treatment with LAM-002A as determined by proteomic tools

Section 6.1.1. LAM-002A Dose Escalation Stage

Change: Based on findings that nausea, vomiting, and diarrhea were treatment-limiting when LAM-002A was given continuously at a dose ≥150 mg twice per day (BID), a plan for further dose exploration using an intermittent LAM-002A dosing regimen with antiemetic and antidiarrheal support was defined (see also Section 6.6). The section was modified accordingly.

The maximum tolerated dose (MTD) will be determined during the dose-escalation stage, evaluating both continuous and intermittent dosing regimens. Subjects will accrue using a 3 + 3 design. During this stage, the decision to open a new cohort at a higher or lower dose level will be made by the participating clinical investigators and sponsor when all subjects in the current cohort have been treated through at least Week 4 or once 2 DLTs have occurred in that dose cohort. All available safety and PK data will be considered in a decision by the medical monitor in collaboration with the investigators to dose escalate, de-escalate, expand the current cohort or explore an alternate regimens schedule of drug administration. The MTD will be determined based primarily on DLTs observed through Week 4 in at least 6 subjects.

Section 6.1.2. Expansion Stage

Change: Based on emerging clinical data, the disease indications to be evaluated in the expansion stage of the study were established. In addition, based on emerging nonclinical data, the combination regimens to be evaluated in the expansion stage were defined. The section was modified accordingly.

Once the MTD and/or recommended phase 2 dose (RP2D) and schedule is determined, the study will enter the expansion stage, in which 3-cohorts of 15-subjects each-will be accrued in order to obtain additional information on safety, tolerability, preliminary anti-tumor activity, PK, and pharmacodynamic data at the RP2D and schedule when LAM-002A is administered alone or in combination with rituximab or atezolizumab. Expansion-stage cohorts will comprise groups of subjects with specific types of previously treated, relapsed, progressive, and measurable NHL who will receive LAM-002A monotherapy or LAM-002A-containing combination therapy as shown in Table 2. For both monotherapy and combination cohorts, the starting dose of LAM-002A will be 125 mg BID administered continuously. The eligibility criteria will remain the same as in escalation but each cohort will be specific to subjects with DLBCL, FL, and CLL/SLL, respectively. The treatment regimen in each of the expansion cohorts will be single agent LAM 002A (apilimod dimesylate capsules) according to the RP2D and schedule.

Version 9, 18 Feb 2020

Table 2: Expansion Stage Disease Types and Therapies

Cohort Number	NHL Type	Investigational Drug	Combination Drug	Evaluable Subjects, n
1	FL	LAM-002A		6
2	MZL	LAM-002A		6
3	DLBCL-GCB	LAM-002A		6
4	DLBCL-ABC	LAM-002A		6
5	FL or MZL	LAM-002A	Rituximab	6
6	DLBCL-GCB or DLBCL-ABC	LAM-002A	Rituximab	6
7	FL or MZL	LAM-002A	Atezolizumab	6
8	DLBCL-GCB or DLBCL-ABC	LAM-002A	Atezolizumab	6

Abbreviations: ABC: activated B-cell (subtype); DLBCL: diffuse large B-cell lymphoma; FL: follicular lymphoma; GCB: germinal center B-cell (subtype); MZL: marginal zone lymphoma; NHL: non-Hodgkin lymphoma

Section 6.1.3. Subject Allocation (Stages 1 and 2)

Change: Consistent with the plan to perform dose-ranging evaluation of intermittent LAM-002A administration and to assess monotherapy and combination therapy cohorts using continuous LAM-002A administration, this section was added to provide information on subject allocation and to describe restrictions to enrollment in Stage 1 and Stage 2 enrollment to enhance study safety.

Subjects will be allocated to the cohorts by the study sponsor working in collaboration with each investigator considering the availability of openings for enrollment in Stage 1 or 2, disease type (i.e., FL, MZL, DLBCL-GCB, DLBCL-ABC, or other indications), therapy history (e.g., prior use of anti-CD20 or anti-PD1/PDL1 antibodies), and current disease status (e.g., potential to benefit from rituximab treatment based on past responses to anti-CD20 antibody therapy).

During Stage 1 dose ranging with LAM-002A monotherapy, allocation will be performed according to a 3+3 dose-escalation procedure with the requirement that each cohort of 3 subjects be observed for \geq 4 weeks before another cohort is enrolled (as detailed in Section 6.6). During Stage 2 cohort expansion evaluating LAM-002A monotherapy, allocation will be performed as subjects present to the accruing clinics and there will be no specific restrictions on the cadence of enrollment. During Stage 2 cohort-expansion of LAM-002A combinations with rituximab and atezolizumab, enrollment of the first 3 subjects in each combination cohort will be restricted such that each subject must be enrolled sequentially and observed for \geq 3 weeks before the next subject is enrolled. Beginning with the 4th patient in each combination group, further enrollment may proceed without restriction as long as the continuous reassessment boundaries for toxic drug discontinuations are not met (as detailed in Section 6.8.2.5 and Section 6.12).

Version 9, 18 Feb 2020

Section 6.1.4 Subject Evaluability

Change: This section was added to clarify subject evaluability for the dose-ranging and cohort-expansion portions of the study.

A Stage 1 subject will be considered evaluable if the subject meets the definition for evaluability of Cycle 1 DLT as described in Section 6.6. A Stage 2 subject will be considered evaluable if the subject has both baseline and ≥ 1 on-study tumor assessments sufficient to allow a determination of response to study therapy.

Section 6.2. Number of Subjects

Change: The number of subjects was updated to reflect the new dose-escalation and cohort-expansion plans.

As many as 110 Approximately 115 evaluable subjects (evaluable subjects include those who complete Cycle 1 dosing [administered at least 75% of doses] and have sufficient safety data, or who are withdrawn from the study due to a DLT in Cycle 1) will be enrolled, assuming that:

- In the dose-escalation stage of the study, the total number of subjects will depend upon the numbers of subjects accrued to each dose level and the number of dose levels evaluated. If 6 subjects are enrolled at all 9 possible open starting dose levels (Dose Levels 5, 6, 7, and 8) and 6 additional subjects are enrolled at the MTD or RD, as many as 60-30 subjects could be enrolled. To allow for the possibility that some subjects may not be fully evaluable for DLT or that an intermediate dose level might be evaluated, up to ~70-45 subjects may be enrolled.
- In the expansion stage of the study, if all 3-8 potential expansion cohorts of 15
 6 evaluable subjects are accrued, as many as 45-48 subjects could be enrolled. To
 allow for the possibility that some subjects may not be fully evaluable for efficacy, up
 to ~55-65 subjects may be enrolled. Subjects will be treated at the RP2D and schedule
 determined in the Dose Escalation Stage of the study.

Section 6.6. LAM-002A Dose-Escalation Procedures

Change: Table 3 was updated consistent with the new dose-escalation and cohort-expansion plans. The initial dose level of the 150 mg BID to be explored with intermittent dosing represented a modest increment over the recommended Phase 2 continuous dosing regimen of 125 mg BID. The text definition of "DLT evaluable" was updated to include the minimum required dosing.

Version 9, 18 Feb 2020

Table 3: LAM-002A Provisional Starting Dose Levels

Continuous Administration		
Dose Level	LAM-002A Dose and Schedule Apilimod Dimesylate Dose mg/dose	LAM-002A Total Daily Dose Apilimod Dimesylate Dose mg/day
-1	25 mg BID	50 mg
0 (Initial Dose Level)	50 mg BID	100 mg
1	100 mg BID	200 mg
1a	125 mg BID	250 mg
1b	75 mg TID	225 mg
1c	100 mg TID	300 mg
1d	125 mg TID	375 mg
2	150 mg BID	300 mg
3	200 mg BID	400 mg
4	275 mg BID	550 mg
Intermittent Administration		
Dose Level	LAM-002A Dose and Schedule	LAM-002A Total Daily Dose
5	150 mg BID	300 mg
6	200 mg BID	400 mg
7	250 mg BID	500 mg
8	300 mg BID	600 mg

Abbreviations: BID: Twice daily (or 2 times per day); TID: Thrice daily (or 3 times per day)

Dose escalation decisions will be evaluated in a DLT-evaluable population. The DLT-evaluable population will include subjects who complete Cycle 1 dosing or who are withdrawn from study due to a DLT in Cycle 1. A subject will be deemed non-evaluable for determining DLTs and will not be counted toward the total cohort size if the subject did not experience a DLT, did not receive at least 75% (42/56 BID schedule; 63/84 TID schedule, 18/24 intermittent schedule) of the planned first-cycle doses or discontinued from the study prior to completing necessary safety evaluations through the first 28 days of study treatment. These subjects may be replaced unless accrual to the cohort has stopped due to DLT.

Section 6.7. Definition of LAM-002A Dose-Limiting Toxicity (DLT)

Change: Information regarding DLT definitions was moved to this section (previously in Section 6.7.2.5) to provide an easier flow of concepts. No changes to the substance of the DLT definitions were made except that the inability to administer the required minimum number of doses on the intermittent schedule due to drug-related AEs was added as a necessary new DLT criterion.

A DLT will be defined as an AE or abnormal laboratory value meeting the criteria in Table 3 and that is assessed as unrelated to disease, a comorbid condition, intercurrent illness, or concomitant medications (see Table 4). For the purposes of dose escalation and determination of the LAM-002A MTDs, DLTs that occur within the first cycle of treatment must be included in decisions regarding dose escalation. DLTs or other clinically significant toxicities that occur after Cycle 1 may also be considered when determining the RP2D.

Version 9, 18 Feb 2020

Table 4: Criteria for Defining Dose-Limiting Toxicities (DLTs)

Toxicity	Criteria
Hematology	CTCAE Grade 4 neutropenia lasting ≥ 7 days CTCAE Grade 4 febrile neutropenia CTCAE Grade 3 thrombocytopenia with bleeding that requires transfusion therapy CTCAE Grade 4 thrombocytopenia
Toxicity	Criteria
Gastrointestinal	≥ CTCAE Grade 3 vomiting or nausea despite the use of optimal anti-emetic treatments ≥ CTCAE Grade 3 diarrhea despite the use of optimal anti-diarrheal treatments
Renal	Serum creatinine > 3.0 x ULN
Hepatica	Total bilirubin \geq CTCAE Grade 3 Total bilirubin \geq CTCAE Grade 2 and ALT or AST \geq CTCAE Grade 2 or, for subjects with liver metastases at baseline, total bilirubin \geq 2.0 x ULN and ALT or AST \geq CTCAE Grade 3
Treatment interruption/delays	Inability to administer ≥28/56 (BID schedule) or ≥42/84 (TID schedule) or ≥12/24 (intermittent schedule) planned LAM-002A doses in a treatment cycle due to drug-related AEs or Failure to recover from apilimod-dimesylate-related toxicities to baseline within 14 days from the last dose of LAM-002A in a cycle
Other adverse events not listed above	 Non-hematologic toxicities of CTCAE ≥ Grade 3 except for the following. alopecia CTCAE Grade 3 fatigue for < 72 hours Asymptomatic Grade 3 elevations in biochemistry laboratory values that last for ≤ 7 days that are not deemed to be clinically relevant. This includes electrolyte abnormalities that respond to medical intervention. Any LAM-002A-related adverse event that, in the opinion of the investigator, requires a dose reduction or discontinuation of treatment.

Abbreviations: ALT: Alanine aminotransferase; AST: Aspartate aminotransferase; CTCAE: Common terminology criteria for adverse events; DLT: Dose-limiting toxicity; ECG: Electrocardiogram; NHL: Non-Hodgkin lymphoma; ULN: Upper limit of normal

Once the RP2D and schedule are established, additional subjects will be treated in 3 histologically distinct dose expansion cohorts designed to better characterize the safety, tolerability, preliminary anti-tumor activity, PK, and pharmacodynamics of the study drug when provided at the MTD (or lower dose per agreement of the Investigators and Sponsor) in a specific B cell NHL subtype. Up to 15 subjects will be treated in each expansion cohort.

Version 9, 18 Feb 2020

Section 6.8.1. Tumor Lysis Syndrome Prophylaxis and Therapy

Change: The heading of the section was changed, as shown above, and information on TLS management was condensed under a single section within the protocol document.

6.8.2 TLS Management

Information regarding TLS prophylaxis is provided in Section 6.6.1.

Subjects who develop TLS may experience hyperkalemia, hypocalcemia, hyperuricemia, hyperphosphatemia, cardiac dysrhythmias, and acute renal failure; thus, close monitoring of electrolytes is important after initial therapy.

Subjects with TLS should receive intravenous hydration, rapid reversal of hyperkalemia, antihyperuricemic agents, and appropriate cardiac and renal support, including dialysis as indicated. Upon recovery to baseline functioning and as medically appropriate, such subjects should continue with protocol therapy to maintain tumor control.

Section 6.8.2. LAM-002A

Change:

Information regarding LAM-002A administration, dose modifications, and supportive care was consolidated in one location in the protocol text, and this section was updated consistent with the new dose-escalation and cohort-expansion plans. The description of the study drug was removed from Section 6.8 and consolidated in a single location in Section 9.1 to avoid redundancy. The types of adverse events typically requiring LAM-002A dose modification were described. Given that LAM-002A has no obvious cumulative toxicity, allowance was made for dose escalation after Cycle 2 of therapy if such an escalation might be medically appropriate considering subject tolerance and antitumor efficacy. More detailed and protocol-specific guidelines for antiemetic prophylaxis and antidiarrheal prophylaxis were included based on current ASCO guidelines.

6.8.2.1. Premedications

Subjects taking LAM-002A by continuous administration may be offered antiemetics and antidiarrheals as necessary to control gastrointestinal symptoms as described in Section 6.8.2.6.1 For subject who do develop such adverse effects, sites should consider providing study participants with antiemetics and antidiarrheals so that these supportive care medications are readily available in case gastrointestinal symptoms related to LAM-002A recur or persist.

Subjects taking LAM-002A by intermittent administration are required to receive prophylactic antiemetic supportive care as described in Section 6.8.2.6.2.

6.7.2. Description of Study Drug

LAM 002A (apilimod dimesylate capsule) is intended for oral administration. Each capsule will contain 25 mg or 50 of apilimod dimesylate (equivalent to 17.1 mg or 34.3 mg of apilimod free base, respectively). The 25 mg capsule is Swedish orange and the 50 mg capsule is white. Both

Version 9, 18 Feb 2020

the 25 and 50 mg capsules are Size 0 and both have a total fill weight of 175 mg. For additional information, see Section 9.1

6.8.2.2. In-Clinic LAM-002A Administration

For subjects receiving the continuous LAM-002A regimen, On Cycle 1 Day 1, and Cycle 1 Day 8 the morning dose of LAM-002A should be orally administered on Cycle 1 Day 1 and Cycle 1 Day 8 (after a minimum fasting state of 6 to 8 hours) by site staff immediately after the collection of the biomarker samples and pre-dose PK sample. Subjects are allowed to eat after PK Sample #4 (Hour 2) has been collected. On Cycle 1 Day 15, the morning dose of LAM-002A should be orally administered (after a minimum fasting state of 6 to 8 hours) by site staff immediately after collection of the pre-dose PK and biomarker samples.

For subjects receiving the intermittent LAM-002A regimen, prophylactic antiemetics are a required component of the regimen as described in Section 6.8.2.5.2. After initiation of the antiemetic regimen, the morning dose of LAM-002A should be orally administered on Cycle 1 Day 1 and Cycle 1 Day 10 (after a minimum fast of 6 hours) by site staff after the collection of the biomarker samples and pre-dose PK sample. Subjects are allowed to eat after PK Sample #4 (Hour 2) has been collected. Similarly, on Cycle 1 Day 8 and Cycle 1 Day 15, the antiemetic regimen should be initiated and the morning dose of LAM-002A should be orally administered (after a minimum fast of 6 hours) by site staff immediately after collection of the pre-dose samples.

When given as a component of combination therapy with rituximab, LAM-002A will be started on Cycle 1 Day 1 with a BID schedule. LAM-002A will be administered after administration of premedications (see Section 6.8.3.1) and ~15 to 30 minutes prior to the start of the initial rituximab infusion. On Cycle 1 Day 8, the morning dose of LAM-002A will be administered after premedications (see Section 6.8.3.1) and ~15 to 30 minutes prior to the rituximab infusion.

When given as a component of combination therapy with atezolizumab, LAM-002A will be started on Cycle 1 Day 1 with a BID schedule. LAM-002A will be administered \sim 15 to 30 minutes prior to the start of the initial atezolizumab infusion. On Cycle 1 Day 8, the morning dose of LAM-002A will be administered \sim 15 to 30 minutes prior to the atezolizumab infusion.

6.8.2.3. LAM-002A Self-Administration

Except for the days where treatment is administered in the clinic, LAM-002A will be self-administered orally, BID or TID of each 28-day cycle until disease progression or other discontinuation criteria are met. When taking the drug at home, subjects should be advised to take LAM-002A with \geq 4 oz. (\sim 160 mL) of water at the same times each day. Subjects on a BID schedule will be advised to take the doses at \sim 12 hours apart (e.g., 8:00 AM and 8:00 PM) (+/-1-hour window). Subjects on a TID schedule will be advised to take the doses at intervals of \sim 6 to 8 hours. When self-administering LAM-002A at home, subjects may take the drug in the fed or fasted state. On PK days, subjects should come to clinic fasted (a minimum fasting state of 6 to 8 hours) and take the dose at the site under supervision. All subjects will be required to complete a dosing diary, which must be returned to the site for review at each site visit.

Version 9, 18 Feb 2020

For those subjects taking LAM-002A with continuous administration, the drug should be taken according the prescribed BID or TID schedule without interruption unless toxicity or intercurrent illness requires a modification to the dosing regimen (see Section 6.8.2.5).

For those subjects taking LAM-002A with intermittent administration, the drug should be taken in repeated 7-day sequences comprising BID self-administration for 3 days (6 doses) followed by 4 days without dosing. If the cadence of the on-off periods is interrupted due to toxicity, intercurrent illness, or other reasons, the medical monitor should be consulted regarding the timing of therapy resumption and dose modification (see Section 6.8.2.5).

6.8.2.4. LAM-002A Dose Schedule Interruptions and Vomited Doses

No changes were made to this section.

6.8.2.5. LAM-002A Dose Modifications

The AEs associated with LAM-002A administration have included gastrointestinal toxicities of nausea, vomiting, and diarrhea, typically beginning shortly after initiation of drug administration.

If a subject experiences an AE that is suspected to be related to LAM-002A, appropriate supportive care (e.g., antiemetics, antidiarrheals, therapy for tumor lysis syndrome [TLS]) should be instituted consistent with the nature of the event.

If a subject experiences an LAM-002A-related DLT (reference Table 3) or other AE requiring a dose modification, then the LAM-002A administration should be interrupted until the toxicity recovers to Grade ≤ 1 or baseline. Upon resumption of LAM-002A, the total daily dose of LAM-002A should be reduced using an appropriate dose level or schedule (reference Table 3) as agreed between the investigator and medical monitor. Successive adjustments to progressively lower total daily dose levels can be made. If the subject cannot tolerate LAM-002A after a decrease to Dose Level -1 (25 mg BID), then the subject should be discontinued from LAM-002A therapy unless continued treatment is permitted by the medical monitor.

After the LAM-002A dose is reduced, the dose can be maintained at that dose level or schedule, even if there is minimal or no toxicity with the reduced dosing regimen. However, if the subject tolerates a reduced total daily dose of LAM-002A for ≥ 4 weeks then the LAM-002A dosing regimen may be reescalated to a higher total daily dose level at the discretion of the investigator and with the concurrence of the medical monitor. Such reescalation may be particularly warranted if the AE comprised TLS or if further evaluation reveals that the AE that led to the dose reduction was not related to LAM-002A. Successive adjustments to progressively higher total daily dose levels can be made. However, the escalated dose cannot exceed the total daily starting dose level for that subject during the first 4-2 cycles of therapy.

Individual subjects who initiated treatment at a total daily dose level **at or** below the lower of the currently established MTD or the RP2D and who have not experienced a DLT after \geq **4-2** cycles of treatment may have the LAM-002A total daily dose escalated to the next higher dose level if both the principal investigator and the medical monitor agree that a dose escalation is medically warranted (e.g., for a subject with stable disease who is tolerating the current dose level of LAM-002A therapy). In such subjects, successive adjustments to progressively higher total daily dose levels can be made at intervals of \geq 4 weeks with the condition that the escalated total daily

Version 9, 18 Feb 2020

dose level cannot exceed a LAM-002A dose of 150 mg BID when administered continuously or the lower of the currently established MTD or RP2D of LAM-002A when given intermittently.

In a subject who experiences a DLT precluding resumption of LAM-002A therapy during a cycle, a new cycle of treatment may begin at the later of Day 29 or when AEs or laboratory abnormalities related to LAM-002A have returned to baseline levels. If drug-related AEs or laboratory abnormalities precluding further administration of study drug are not resolved to baseline by Day 29, week-by-week delays in initiating the new cycle of treatment should be instituted. When all drug-related AEs and laboratory abnormalities have returned to baseline, the next cycle of therapy can be initiated. Upon initiation of a new cycle of therapy, the prior cycle of therapy will be considered completed.

Investigators are to discuss modifications in the dosing regimen with the medical monitor. The appropriate clinic staff should dispense the LAM-002A for the new dose level or schedule and instruct the subject/caregiver about the change in the dosing regimen.

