1.5 Definitions of Tumor Response and Progression

Responses will be categorized as complete response (CR), partial response (PR), stable disease (SD), or progressive disease (PD). In addition, a response category of nonevaluable (NE) is provided for situations in which there is inadequate information to otherwise categorize response status.

The best overall response will be determined. The best overall response is the best ontreatment response from baseline recorded from the start of treatment until PD/recurrence. The baseline measurement will be taken as a reference for determinations of response. The nadir measurement will be taken as a reference for PD; this measurement constitutes the smallest measurement recorded, including the baseline measurement if this is the smallest measurement. For FDG-avid tumors, metabolic criteria for response by PET-CT will take precedence over anatomic criteria for response by contrast CT when assessing CR.

Version 9, 18 Feb 2020

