- K Assessment of disease status will be conducted with standard clinical measurements: PE, CBCs, bone marrow aspirates/biopsies, and imaging as appropriate for indication. During treatment, scans will be repeated for tumor assessment within 7 days of Day 1, Cycles 3, 5, and 7 then every 3 months until PD or use of alternative antineoplastic therapy. For subjects still in response after 1 year, intervals for radiographic surveillance may be every 6 months. Subjects with CLL who achieve CR will require assessment of MRD by flow cytometry of bone marrow and peripheral blood.
- L Imaging at EOT is not required if PD has already been radiographically documented or last imaging was within 30 days of EOT visit.
- M Subjects with CLL/SLL must provide either a fresh blood sample containing circulating tumor cells or a bone marrow aspirate sample pretreatment. Tissue will be submitted for evaluation of the percentage of tumor cells and analysis of genetic alterations and/or gene expression that may predict anticancer activity and/or pharmacodynamic activity. In addition, for subjects with CLL/SLL, the sponsor may arrange for a portion of the sample to be evaluated at a sponsor-specified laboratory for known prognostic markers (e.g., quantitative immunoglobulins, FISH panel [chromosome 11q deletion, 13q deletion, 17p deletion and 12 trisomy], DNA mutational analysis for p53, IgHV [including IgHV3-21], and other genes of interest in CLL [e.g., Notch]; flow cytometry [for CD5, CD10, CD11c, CD19, CD20, CD23, CD38, CD45, kappa and lambda light chains and ZAP-70], and/or β2-microglobulin). The baseline bone marrow aspiration procedure (if required) should be performed after the study candidate has undergone the baseline radiology examination and is otherwise considered eligible for study participation. All subjects with CLL/SLL must have baseline imaging (with CT scans [preferred] or MRI scans).

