Change: The protocol was modified to permit evaluation of single-agent LAM-002A or the LAM-002A/rituximab combination in additional patients with FL. Use of either intravenously administered rituximab or subcutaneously administered rituximab hyaluronidase human was permitted.

Once the MTD and/or recommended phase 2 dose (RP2D) and schedule is determined, the study will enter the expansion stage, in which cohorts of subjects will be accrued in order to obtain additional information on safety, tolerability, preliminary anti-tumor activity, PK, and pharmacodynamic data at the RP2D and schedule when LAM-002A is administered alone or in combination with rituximab/rituximab hyaluronidase or atezolizumab. Expansion-stage cohorts will comprise groups of subjects with specific types of previously treated, relapsed, progressive, and measurable NHL who will receive LAM-002A monotherapy or LAM-002A-containing combination therapy as shown in Table 2. For both monotherapy and combination cohorts, the starting dose of LAM-002A will be 125 mg BID administered continuously.

Version 9, 18 Feb 2020

Table 2: Expansion Stage Disease Types and Therapies

Cohort Number	NHL Type	Investigational Drug	Combination Drug	Evaluable Subjects, n
1	FL	LAM-002A		6 Up to ~20
2	MZL	LAM-002A		6
3	DLBCL-GCB	LAM-002A		6
4	DLBCL-ABC	LAM-002A		6
5	FL or MZL	LAM-002A	Rituximab or rituximab hyaluronidase human	6 Up to ~20 with FL
6	DLBCL-GCB or DLBCL-ABC	LAM-002A	Rituximab or rituximab hyaluronidase human	6
7	FL or MZL	LAM-002A	Atezolizumab	6
8	DLBCL-GCB or DLBCL-ABC	LAM-002A	Atezolizumab	6

Abbreviations: ABC: activated B-cell (subtype); DLBCL: diffuse large B-cell lymphoma; FL: follicular lymphoma; GCB: germinal center B-cell (subtype); MZL: marginal zone lymphoma; NHL: non-Hodgkin lymphoma

Section 6.2 Number of Subjects

Change: Information regarding the total potential accrual to the study was updated consistent with modifications to the protocol to evaluate single-agent LAM-002A or the LAM-002A/rituximab combination in additional patients with FL.

As many as $\underline{145}$ $\underline{110}$ subjects will be enrolled, assuming that:

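### Responses first seen after permitted escalation to 150 mg BID would, on the visible text, enter a response rate described as activity at the 125 mg BID recommended dose

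*Combined protocol and SAP*

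**What the plan says.** All of the following is text inserted or retained in the amendment entries and Appendix 2. The entry for Section 6.8.2.5 is from Amendment 6, and no later visible amendment changes it.

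- **Recommended dose.** The Amendment 6 entry for Section 6.6 refers to "the recommended Phase 2 continuous dosing regimen of 125 mg BID". Section 6.1.2, as repeated in the later amendment that enlarged the FL cohorts, says: "For both monotherapy and combination cohorts, the starting dose of LAM-002A will be 125 mg BID administered continuously". The same section describes Stage 2 as gathering safety and preliminary activity data at the recommended dose and schedule.
- **Finding at the higher dose.** The Amendment 6 entry for Section 6.1.1 gives as its reason for change that "nausea, vomiting, and diarrhea were treatment-limiting when LAM-002A was given continuously at a dose ≥150 mg twice per day (BID").
- **Escalation rule.** Section 6.8.2.5 applies to subjects who started at or below the lower of the MTD or RP2D and have had no DLT after at least 2 cycles. They may be escalated if the principal investigator and medical monitor agree that it is medically warranted. The example is a subject with stable disease who tolerates the current dose. The continuous limit is that the escalated total daily "dose level cannot exceed a LAM-002A dose of 150 mg BID when administered continuously".
- **Response definition.** Appendix 2, Section 1.5: "The best overall response is the best ontreatment response from baseline recorded from the start of treatment until PD/recurrence".
- **Scan timing.** Section 8.7, Table 8, footnote k: "scans will be repeated for tumor assessment within 7 days of Day 1, Cycles 3, 5, and 7", then every 3 months.
- **Evaluability and decision lists.** Section 6.1.4 requires a baseline and at least one on-study tumor assessment. Section 14.1.2 lists the n/N pairs at which FL accrual is considered sufficient. Neither mentions dose.

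**The concern.** The response rate may mix two doses, and who moves to the higher one depends on outcome. Escalation opens after 2 cycles, which is when the first on-treatment scan falls, and the plan's own example is a subject whose disease is stable. Subjects without a response at the first scan are therefore the natural candidates. Their Cycle 5, Cycle 7 and later scans may then be read on 150 mg BID.

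If such responses are pooled without comment, a rate presented as activity at 125 mg BID could owe part of its value to a higher dose, one that the same amendment reports as hard to tolerate when given continuously. The reverse applies to safety. The rule is not confined to monotherapy, and the combination-group monitoring of AE discontinuations in Section 14.1.2 also carries no dose condition. An event arising after escalation would enter the same count as one on the starting dose.

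**Working it through.** **1. Is the path open?** Table 3 in Section 6.6 puts 125 mg BID at 250 mg/day and 150 mg BID at 300 mg/day, the next BID step. An expansion subject starts at the RP2D, so the condition of starting at or below it is met. The limit of 150 mg BID permits the step. The path is open, subject to the conditions above.

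**2. Which responses are affected?** With 28-day cycles, 2 cycles end on Day 56 and Cycle 3 Day 1 is Day 57. The first scan, within 7 days of that date, falls at about the earliest possible escalation. Responses already documented then are largely unaffected. Those first seen at the Cycle 5 scan (about Day 113) or later can be.

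**3. The plan's own figures (Section 14.1.2), reproduced.** Exact binomial bounds for x responses in n subjects:

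- Lower one-sided 95% bound = 0.05 quantile of Beta(x, n − x + 1).
- Upper one-sided 90% bound = 0.90 quantile of Beta(x + 1, n − x).

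For FL monotherapy the plan states a lower bound of at least 20% for every listed pair. Of the 17 pairs, 16 give at least 0.20, and 5/11 gives 0.1996, which rounds to 20%. For 0/6 the upper bound is 1 − 0.10^(1/6) = 0.319, matching the stated 32%.

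**4. Effect of one response.**

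| Count | Bound | One response different | Bound |
|---|---|---|---|
| 8/20, FL monotherapy | lower 21.7% | 7/20 | lower 17.7% |
| 12/20, FL with rituximab | lower 39.4% | 11/20 | lower 34.7% |
| 0/6, small cohort | upper 32% | 1/6 | upper 51% |

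Removing one response from any listed monotherapy pair gives a lower bound between 12.9% and 19.96%, below the 20% criterion. Doing the same on the combination list gives 30.4% to 36.8%, below its 39% criterion. In a 6-subject cohort, one post-escalation response is enough to stop an ORR of 35% from being excluded.

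**5. Illustration, on assumed inputs.** The documents give no escalation frequency and no response rate after escalation. Suppose the true ORR at 125 mg BID is 20%, and a fraction q of the remaining subjects respond only after escalation. The pooled rate is 0.20 + 0.80q. The chance of at least 8/20 at the final count, ignoring earlier looks, is:

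| q | Pooled ORR | P(X ≥ 8 of 20) |
|---|---|---|
| 0 | 20% | 0.032 |
| 0.05 | 24% | 0.083 |
| 0.10 | 28% | 0.171 |
| 0.20 | 36% | 0.436 |

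This shows sensitivity and is not a forecast. It also credits every later response to the higher dose, although some might have occurred at 125 mg BID.

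**The case against.** The strongest reply is that the ORR describes a regimen, not a fixed dose. Section 6.1.2 calls 125 mg BID a starting dose, the modification rules belong to the regimen, and the FL paragraphs in Section 14.1.2 speak of activity with the two regimens. Counting best response under the protocol-defined regimen is a legitimate treatment-policy summary. This stands, and it is why the all-doses rate should be kept. It does not remove the need for a label, because Section 6.1.2 describes the data as belonging to the recommended dose and schedule.

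Dose reductions, which Section 6.8.2.5 allows down to 25 mg BID, also mix doses. That is true, but reductions follow toxicity, whereas the escalation example turns on the absence of a response.

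Three stronger readings are tempting and not supported:

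- **That the plan states that later responses count as activity at the RP2D.** This is inferred from the lack of a dose condition. Only the second part of the document is available, and the current full text of Sections 6.8.2.5 and 14.9 is not shown. The Appendix 2 response wording also predates the Amendment 6 expansion design.
- **That the 150 mg BID ceiling is simply an error.** The rule requires no DLT and joint agreement. Section 6.8.2.5 says gastrointestinal events typically begin soon after treatment starts, and Amendment 6 gives a reason: no obvious cumulative toxicity. These points address tolerability. They do not say how later responses are attributed.
- **That the n/N lists are binding go decisions.** They mark when accrual can be considered sufficient, and an ORR of 40% or more would only suggest further development.

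**Conclusion.** The point holds as a gap in attribution. Escalation from the RP2D to 150 mg BID continuous is permitted, the same amendment calls that continuous dose treatment-limiting, and no visible text separates responses before and after escalation. The ORR criteria are sensitive enough for this to matter: one response moves 8/20 from a lower bound of 21.7% to 17.7%, and separates 0/6 (upper bound 32%) from 1/6 (51%).

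The conclusion assumes that no attribution rule stands in the part of the document not shown. The size of any actual effect is unknown, because the frequency of escalation is not documented. Confidence is high on the permitted path and the sensitivity, and lower on the absence of a rule. Cycle 1 DLT assessment is not affected, since escalation follows at least 2 cycles. No view is taken on which dose rule is right.

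**What to change.** In Section 14.1.2 and the efficacy analysis:

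1. Keep best overall response across all doses, labelled as the result of the regimen with permitted escalation.
2. Alongside it, report the ORR and the FL n/N comparison counting only responses first documented before any escalation above 125 mg BID.
3. State that activity at the RP2D is concluded only if the two agree or the difference is explained.
4. Tabulate adverse events and AE discontinuations by LAM-002A dose at onset, in monotherapy and combination cohorts.

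Separately, the sponsor should reconcile the Amendment 6 reason for change in Section 6.1.1, the starting dose in Section 6.1.2 and the continuous ceiling in Section 6.8.2.5.

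The cost is a little extra analysis from dosing dates already recorded. The pre-escalation ORR will be conservative, because it leaves out late responses that might have occurred at 125 mg BID anyway. For that reason it should accompany the all-doses rate and not replace it.
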